4.3 Analysis of Safety

4.3.1 Preliminary Safety Assessment Phase

An initial assessment of the proportion of patients free from complications due to unnecessary procedures resulting from false positive events will be conducted on the first 500 patients to complete 6 months of follow-up. In patients with an upgraded Fortify[®] ST device, the 6 months of follow-up begins with either their Baseline visit or the Baseline Upgrade visit (during which the firmware upgrade occurs). In patients with Fortify Assura ST[®] and Ellipse ST[®], the 6 months of follow-up begins with the Baseline visit. For those patients with Fortify Assura ST[®] and Ellipse ST[®], the survival time for patients who experience a complication will be calculated as the number of days from the Baseline visit (when the Patient Notifier is activated) to the date of the procedure-related complication. For those patients with Fortify[®] ST devices, the survival time will be calculated as the number of days from either the Baseline visit or the Baseline Upgrade visit (i.e., whichever visit the patient received the firmware upgrade) to the date of the procedure-related complication is first discovered. For patients who withdraw without experiencing a complication prior to analysis, their survival time will be censored at the date of withdrawal. For patients who have not experienced complications at the time of analysis, their survival time will be censored on the date of the analysis.

All patients who have the Patient Notifier turned ON at the Baseline visit or the Baseline Upgrade visit and have completed their 6-month follow up visit or 6 months of follow up since being upgraded will be included in this analysis.

Statistical Analysis Plan

Complications related to unnecessary procedures resulting from false positive events are defined as any procedure-related or test-related complications that occur in a patient in which a Type I ST episode is classified as a false positive according to the criteria described in section 3.2.3. All clinical events will be adjudicated by an independent and blinded Clinical Event Committee for the purposes of determining whether the event was related to ischemia or acute coronary syndrome and whether it was procedure or test related. Complications related to procedures or tests may include, but are not limited to:

- Air embolism
- Allergic reaction to contrast media
- AV fistula
- Bleeding
- Cardiac tamponade
- Contrast nephropathy

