4.3.2 Primary Safety Endpoint

The ST Monitoring Feature will be evaluated by the percentage of patients with false positive events. The percentage of patients with false positive events is calculated as the number of patients who experience false positives divided by the number of evaluable patients. A False Positive occurs when a clinical event does not occur within 72 hours following a Type I ST episode.

The hypothesis is formally expressed as follows:

H_0 : Percent of patients experiencing a false positive event in 12 months $\geq 15\%$

H_a : Percent of patients experiencing a false positive event in 12 months $< 15\%$

The desired outcome is to reject the null hypothesis at the 2.5% significance level. The null hypothesis will be rejected at the 2.5% significance level if the

Statistical Analysis Plan

upper bound of the 95% confidence interval for the percent of patients experiencing false positive events is less than 15%. The upper confidence bound will be calculated using the Wilson score interval method.

Patient Group

All enrolled patients who have a successful implant or system revision, complete the baseline follow up visit and have the ST Monitoring Feature and Patient Notifier turned ON will be included in the evaluation of this study endpoint. Data collection towards the study endpoint will begin after the Baseline visit.

Further, the analysis population for the primary safety endpoint will be those subjects with the Fortify[®] ST (upgraded), Fortify Assura[®] ST and Ellipse[®] ST. Data from subjects with a Fortify[®] ST device prior to being upgraded will not be included in this analysis.

Analysis

Primary Analysis

The primary analysis will be a complete case analysis where patients who are lost to follow-up before completing their 12 month visit without experiencing a false positive event will be considered non-evaluable and omitted from the analysis of the endpoint. Patients experiencing a false positive event and withdrawing before the 12 month visit will be included in the analysis. The proportion of patients experiencing false positives will be estimated by the number of patients experiencing a false positive event divided by the number of evaluable patients.

Imputation Analysis

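### Section 4.3.2 gives no time zero for Fortify ST patients upgraded after Baseline; if their 12 months run from Baseline, short exposures count as full false-positive-free years

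*Protocol*

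**What the plan says.** The Protocol and SAP carry the same text here.

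- **Hypothesis (4.3.2).** The null and alternative concern the "Percent of patients experiencing a false positive event in 12 months", with 15% as the boundary. The null is rejected if the Wilson "upper bound of the 95% confidence interval for the percent of patients experiencing false positive events is less than 15"%.
- **Start of data collection (4.3.2).** "Data collection towards the study endpoint will begin after the Baseline visit". The Baseline Upgrade visit is not mentioned anywhere in this section.
- **Exclusion (4.3.2).** "Data from subjects with a Fortify[®] ST device prior to being upgraded will not be included in this analysis".
- **Evaluability (4.3.2).** In the primary, complete-case analysis, "patients who are lost to follow-up before completing their 12 month visit without experiencing a false positive event will be considered non-evaluable". By implication, a patient who reaches that visit without a false positive is evaluable. No minimum time since the upgrade is set.
- **Estimator (4.3.2).** Patients with a false positive divided by evaluable patients, with no allowance for exposure.
- **Preliminary assessment (4.3.1).** For Fortify ST patients the clock starts at the Baseline or the Baseline Upgrade visit, whichever delivered the firmware upgrade. Patients qualify by completing the 6-month visit or, as an alternative, "6 months of follow up since being upgraded will be included in this analysis".

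**The concern.** Section 4.3.1 shows that the authors foresaw upgrades after Baseline and adapted both time zero and the eligibility rule to them. Section 4.3.2 keeps the exclusion of pre-upgrade data but not the matching change of clock. If the 12 month visit stays tied to the original Baseline, removing pre-upgrade data shortens the window in which a late-upgraded patient can have a false positive, while the patient still counts as one whole person in the denominator. Someone upgraded 8 months after Baseline would enter as free of false positives for 12 months on 4 months of admissible data.

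The hypothesis is about 12 months, and the goal is met when the percentage is low. This mechanism therefore pushes toward declaring success on the primary safety endpoint. The other planned analyses do not repair it. The imputation covers only non-evaluable patients, and these patients are classed as evaluable. The bootstrap reuses the same estimator.

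**Working it through.** **1. Which anchor does the text imply?** Section 4.3.1 lists completion of the 6-month visit and 6 months since the upgrade as two alternatives, so a scheduled visit is not treated there as the same thing as time since upgrade. Section 4.3.2 uses only a scheduled visit, the 12 month visit, and begins collection at Baseline. Counting from Baseline is thus the natural reading. No sentence states it.

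**2. The plan's own figures.** The sample-size text for this endpoint is redacted, and the visible total of 5,228 is driven by the efficacy endpoint, so there is no safety calculation to reproduce. The decision rule can be reproduced. With 1,000 evaluable patients the Wilson upper bound is below 15% for at most 127 patients with a false positive, and the chance of that at a true 15% is 2.1%. With 5,228 the limit is 733 and the chance is 2.4%. Both agree with the nominal 2.5%.

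**3. Assumptions for the size.** These are not in the documents.
- The true 12-month risk is exactly 15%, with a constant hazard.
- A share f of evaluable patients is upgraded after Baseline.
- Each of these has m post-upgrade months before a 12 month visit counted from Baseline.

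**4. Risk over a shortened window.** Risk(m) = 1 − 0.85^(m/12).
- m = 3: 4.0%
- m = 6: 7.8%
- m = 9: 11.5%

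**5. Expected observed percentage.** (1 − f) × 15% + f × risk(m). For m = 6:
- f = 10%: 0.90 × 15% + 0.10 × 7.8% = 14.28%
- f = 25%: 0.75 × 15% + 0.25 × 7.8% = 13.20%

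**6. Chance of a false pass.** This is the binomial probability of at most 127 patients with a false positive out of 1,000, at the expected percentage. Each cell shows the expected percentage, then that chance.

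| f | m = 3 | m = 6 | m = 9 |
|---|---|---|---|
| 5% | 14.45%; 6.1% | 14.64%; 4.3% | 14.82%; 3.1% |
| 10% | 13.90%; 14.7% | 14.28%; 8.2% | 14.65%; 4.3% |
| 25% | 12.25%; 69% | 13.20%; 34% | 14.12%; 10.6% |
| 50% | 9.49%; >99% | 11.40%; 91% | 13.24%; 33% |

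With 5,228 evaluable patients, an upper limit because it is the planned enrolment, the m = 6 figures for f = 5%, 10% and 25% are 10.6%, 30% and 96%. With f = 0, or with every upgrade at the Baseline visit, there is no bias.

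**7. A repair that does not work.** Suppose short-exposure patients without a false positive were made non-evaluable, while those with one stayed in. For m = 6 the percentage becomes [(1 − f) × 0.15 + f × 0.078] / [(1 − f) + f × 0.078]:
- f = 10%: 0.1428 / 0.9078 = 15.7%
- f = 25%: 0.1320 / 0.7695 = 17.2%

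That selects on the outcome and overstates a true 15%.

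**The case against.** A reader might infer that the plan definitely leaves the clock at Baseline and that the primary safety result is therefore biased low. The documents do not support that. Section 4.3.2 never says from which visit the 12 month visit is counted for upgraded patients. The hypothesis refers to 12 months, and section 3.1 defines the endpoint over the 12 months after a 3-month run-in. Together with the exclusion of pre-upgrade data, this could mean 12 included months. The visit schedule may also be settled in the investigational protocol cited in 4.7.10, or in the flow diagram, which the public copy does not show. This stands: the bias is conditional on the anchor.

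A reader might also infer that the goal would wrongly be met. The share and timing of later upgrades are unknown, and Fortify ST patients upgraded at Baseline lose no exposure. With few or early upgrades the distortion is small, and a hazard concentrated soon after the upgrade would shrink it further. This stands too.

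The net direction for the whole endpoint is not fixed either. The same complete-case rule drops losses without a false positive and keeps those with one, which pushes upward. If 10% are lost uniformly over 12 months under a true 15% and constant hazard, their mean risk is 1 − 0.15/0.1625 = 7.7%, and the percentage becomes (0.135 + 0.0077)/(0.90 + 0.0077) = 15.7%. That is a separate effect of unrelated size and cannot be relied on to cancel this one.

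Finally, a reader might extend the point to the false positive rate in 4.3.3. That rate is per patient-year and already excludes pre-upgrade data. If pre-upgrade person-time goes with it, the rate largely corrects itself.

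**Conclusion.** The point holds in conditional form. Section 4.3.2 leaves time zero and evaluability undefined for patients upgraded after Baseline, although 4.3.1 defines both for the preliminary assessment. On the natural reading, these patients count as 12-month successes on less than 12 months of data, and this mechanism can only lower the percentage.

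Its size rests on an assumed constant hazard and on a share and timing of upgrades that the documents do not give. Across later-upgraded shares of 5% to 25% and 3 to 9 post-upgrade months, a true 15% would be expected to show as 14.8% down to 12.3%. The false-pass chance with 1,000 evaluable patients would run from 3% to 69%. It should be corrected before analysis, because otherwise the anchor could be chosen with the data in view.

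**What to change.** In 4.3.2 of the Protocol and SAP:

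- State that time zero for upgraded Fortify ST patients is the Baseline or Baseline Upgrade visit at which the firmware upgrade was received, as in 4.3.1.
- Estimate the 12-month percentage by Kaplan-Meier from that date, censoring patients with shorter post-upgrade follow-up. The Wilson bound does not apply directly to such an estimate, so name the interval; 4.3.1 already uses Greenwood's variance.
- Alternatively, keep the simple proportion and the Wilson bound, but follow all upgraded patients to 12 months after the upgrade before the data cut. At a true 15% the expected percentage is then 15.0%.
- Do not drop short-exposure patients without a false positive while keeping those with one.
- Report how many patients were upgraded after Baseline and their post-upgrade exposure.
- In 4.3.3, only confirm that pre-upgrade person-time is excluded. The estimator need not change.

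The cost is a few sentences, plus either a slightly wider interval or longer follow-up for some upgraded patients. Protocol section 4.5 already continues follow-up until study closure, but waiting for 12 post-upgrade months could delay the data cut, which depends on the primary safety data being available.

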- Formation of hematomas or cysts
- Infection
- Myocardial infarction
- Peripheral nerve injury
- Pneumothorax
- Pseudo-aneurysm
- Stent thrombosis
- Stroke
- Thromboemboli
- Venous occlusion
- Venous or cardiac perforation

Analysis

- A Kaplan-Meier estimate of the proportion of patients free from complications arising from a false positive event through the 6 month follow-up visit will be provided with a 95% lower bound on the estimate using Greenwood's formula for the variance of the Kaplan-Meier estimator. If no events have been observed, then a Clopper-Pearson 95% exact lower confidence bound for the proportion of patients free from complications due to unnecessary procedures resulting from false positive events will be provided.
- A tabular presentation of ER visits, doctor office visits, or any medical care will be presented, stratified by false positive, true positive and false negative events.
- The proportion of patients with false positive events, with the count of false positive, true positive and false negative events will be provided. A preliminary estimate of sensitivity will be calculated.
- The proportion of patients with the ST monitoring feature turned off after the Programming and Baseline visits will be tabulated along with the reason for the turning off the ST monitoring feature.
- Baseline demographics and site enrollment will be tabulated.

Statistical Analysis Plan

The above analyses will be presented overall and by the following subgroups:

- Coronary artery disease patients with cardiomyopathy
- Coronary artery disease patients without cardiomyopathy
- Patients with abnormal baseline ECGs, for each of six abnormal subgroup categories
- Patients with normal baseline ECGs
- Patients with arrhythmias
- Gender
- Patients alerted via Merlin.net and patients alerted via device Patient Notifier

Additional Analysis

An analysis will be performed that includes all clinical events using a GEE logit-link linear model to estimate the sensitivity with a working correlation that provides a robust estimator of the variance adjusting for multiple clinical events within patients.

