A comparison of baseline characteristics of the subjects with missing data and those without missing data will be done to determine if there is evidence that the data are not missing at random (it is not possible to determine that data are missing at random). If the missing at random assumption is clearly violated by these comparisons, it is usually possible to find a sub-group that are not missing at random who have to be imputed differently, such as assigning the worst score to patients in the sub-group. If this resolves the missing at random difficulty, the sub groups will be given special scores and the remaining patients will be imputed as described above.

This analysis will use the patients from the complete case analysis to perform a logistic regression and an imputation procedure to impute false positive status for patients who were non-evaluable in the complete-case analysis. The imputations are described as follows: A logistic regression will be performed using the complete case patients, with the dependent variable dichotomous

Statistical Analysis Plan

false positive status and the independent variables for ischemic Cardiomyopathy and each of the four categories of non-ischemic Cardiomyopathies (Dilated, Hypertrophic, Restrictive and ARVD), age, gender, QRS duration > 120ms and EF% at the time of enrollment. The estimates of the coefficients and standard errors of the logistic regression will be used as the parameters of a multivariate normal distribution that will define the population of the logistic regression model parameters. Up to ten random samples logistic model parameters will be selected. For each random set of parameters, the non-evaluable patients will have their false positive status imputed as having experienced a false positive if their predicted logistic model response is >0.5, and not having experienced a false positive event otherwise. These imputed datasets will be created using PROC MI in SAS V9.2 or greater. An analysis of the hypothesis will be carried out for each complete imputed dataset, and the results will be combined across datasets to obtain one overall conclusion using PROC MIANALYZE in SAS V9.2 or greater.

Additional Analysis

[figure not shown]

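### The primary safety complete-case rule overstates the 12-month false positive percentage when loss is unrelated to false positive risk, and the planned >0.5 imputation overcorrects to a value that is too low

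*Protocol*

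**What the plan says.** Section 4.3.2 (same text in both documents) sets the null hypothesis on "Percent of patients experiencing a false positive event in 12 months" at 15% or more. It rejects at 2.5% if the upper limit of the two-sided 95% Wilson interval is below 15%.

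The primary analysis is complete-case, with two rules for early leavers. Those with no FP are dropped: "patients who are lost to follow-up before completing their 12 month visit without experiencing a false positive event will be considered non-evaluable". Those with an FP are kept: "Patients experiencing a false positive event and withdrawing before the 12 month visit will be included in the analysis". The bootstrap analysis reuses this estimator.

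For the imputation analysis, "A logistic regression will be performed using the complete case patients" on baseline covariates. Model parameters are drawn up to ten times, and each non-evaluable patient is classed as "having experienced a false positive if their predicted logistic model response is >0.5, and not having experienced a false positive event otherwise". If missing at random is clearly violated, a subgroup may be handled differently, "such as assigning the worst score to patients in the sub-group".

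Section 4.3.1 plans a time-to-event method for another safety measure: "A Kaplan-Meier estimate of the proportion of patients free from complications arising from a false positive event through the 6 month follow-up visit". Its set is limited to patients who "have completed their 6-month follow up visit or 6 months of follow up since being upgraded will be included in this analysis", although withdrawals are to be censored.

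The sample-size text for this endpoint is redacted, and a figure is missing under its additional analyses.

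**The concern.** The hypothesis is about the percentage with an FP over 12 months. The two rules for leavers count the FPs that leavers had and discard the FP-free time of the other leavers. If loss is unrelated to FP risk, that pushes the percentage up. The imputation analysis should show how much this matters, but a cut at 0.5 when risk is near 15% turns almost every leaver into a non-event and pushes the result below the truth.

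Near the 15% goal, a feature that is truly below it can therefore miss because of dropout, while the sensitivity analysis can seem to meet the goal with the truth on the boundary. The two results would disagree because of their rules and not because of the device.

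**Working it through.** **Inputs.** From the documents: goal 15%, one-sided 2.5%, Wilson interval, 12-month window, and the rules above. Assumed, because the text is redacted: 12-month loss L of 5/10/15/20%, 3,000 evaluable patients, and true 12-month FP risk p of 11% to 15%. Every FP-free leaver, including deaths and withdrawals, is taken as dropped.

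**The plan's own figure.** (1 − 0.95)/2 = 2.5%, as stated. The Wilson rule passes with at most 411 FP patients of 3,000 (127 of 1,000; 628 of 4,500). With no loss and p = 15%, the exact chance of 411 or fewer is 2.3%, so the test itself is sound.

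**Direction, any hazard shape.** Let G(t) be the probability of still being followed at t, independent of the time to first FP, and A = ∫G dF over 12 months the share with an observed FP. The complete-case value is A/(A + (1−p)G(12)). Since G(t) ≥ G(12), A ≥ pG(12), so this value is at least p. Setting all leavers to no FP gives A, which is at most p.

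**Size, constant hazards.** With 12 months = 1, h = −ln(1−p) and d = −ln(1−L):

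- F = h/(h+d) × (1 − exp(−(h+d))), FP observed
- C = exp(−(h+d)), completed without FP
- m = 1 − F − C, lost without FP
- complete-case = F/(F+C); all leavers set to no FP = F

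Example, p = 13%, L = 10%: h = 0.1393, d = 0.1054, F = 0.1235, C = 0.7830, m = 0.0935. Complete-case = 0.1235/0.9065 = 13.6%. The chance of 411 or fewer of 3,000 is 56%.

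| Loss | 5% | 10% | 15% | 20% |
|---|---|---|---|---|
| True 13%, complete-case reads | 13.3% | 13.6% | 14.0% | 14.4% |
| Passes (88% with no loss) | 75% | 56% | 34% | 15% |
| True 12%, complete-case passes | 99% | 97% | 90% | 76% |
| True 15%, leavers imputed no FP, reads | 14.6% | 14.3% | 13.9% | 13.5% |
| Imputation analysis meets the 15% rule | 8% | 22% | 47% | 74% |

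At true 11%, 99% still pass at 20% loss. The imputation rows use all N = 3,000/(F+C) = 3,145/3,306/3,483/3,682 patients and assume that no predicted risk exceeds 0.5.

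**Does anyone cross 0.5?** To cancel the shortfall at true 15%, (p − F)/m, about 8% of leavers, would have to be imputed as FP. In simulations with covariate-driven risk (model AUC up to 0.82, 10–20% loss, parameter draws using the full covariance matrix), 0–4.9% were, and the imputed estimate was 13.4–14.7%. If none cross, the imputed datasets are identical and the between-imputation variance is zero.

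**Would random draws from the same model help?** No. Without covariates they give F + m × F/(F+C) = F/(F+C), the complete-case value again. Draws conditional on each leaver's FP-free time return p.

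**Leavers at higher risk.** A share L leaves at uniform times with FP hazard r times that of stayers, and overall risk is fixed at 13%. The complete-case bias is zero at r = 2.05/2.17/2.32/2.51 with constant hazard, at 3.2–4.9 if FPs come early (Weibull shape 0.5) and at 1.5–1.7 if they come late (shape 2). Above that ratio the rule understates.

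**Time to first FP, leavers censored, log-log limits (simulation, 3,000 expected evaluable).** With 0–20% unrelated loss it passes 88–91% at true 13% and 2.2–2.7% at true 15%. At r = 2 and true 15%, it passes 6/14/24% at 5/10/15% loss; the complete-case rule passes 2/2/1%.

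**The case against.** The strongest reply is that the primary rule errs on the safe side. For a single-arm safety goal, overstating harm is defensible, and a censoring estimator as primary would be less conservative if leavers are at higher risk. That stands, so replacing the primary analysis is a choice and not a necessity.

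A reader might infer that the trial could wrongly declare its primary safety goal met. The documents do not support this: the complete-case analysis is the primary test, and the 8/22/47/74% belong to a sensitivity analysis.

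The low bias of the imputation needs few predicted risks above 0.5. The plan names coefficients and standard errors but not covariances. If draws ignore covariances, simulated imputed means at true 15% were 14.9–15.8% with 1,000 patients, so the bias can vanish by accident; with 4,000 they stayed at 13.5–14.9%. The worst-score option could also raise the figure, but it applies only when missing at random is clearly violated.

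The size is uncertain. If FP-free deaths or withdrawals count as evaluable, the upward bias shrinks; the omission rule mentions only loss to follow-up. A reader might also conclude that no adequate analysis is planned. Redacted text and a missing figure prevent that conclusion.

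In 4.3.1, completers-only selection and censoring of withdrawals need not conflict: a patient can finish 6 months and withdraw before the analysis date. The wording still leaves out a complication that ends participation before 6 months.

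**Conclusion.** The concern holds in this form. Under loss unrelated to FP risk, the primary rule overstates the 12-month percentage for any hazard shape, by about 0.3 to 1.4 points at true 13% and 5–20% loss. That costs much of the chance of success near the goal and little at true 11% or below. The direction reverses if leavers have enough extra FP hazard, and the break-even ratio depends on when FPs occur.

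The imputation analysis does not repair this. When few predicted risks exceed 0.5, as expected near 15%, it reads low by about 0.4 to 1.5 points at true 15%, which favours passing. This is the more important defect, because the analysis meant to test robustness errs in the unsafe direction.

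The direction is certain under the stated conditions. Confidence in the size is moderate, because loss rates and patient numbers are assumptions and text that is not visible may add analyses.

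**What to change.** In SAP 4.3.2:

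- **Imputation.** Replace the >0.5 cut with random draws from a time-to-event model conditional on each leaver's FP-free time. Multiply leavers' later FP hazard by, for example, 1, 1.5, 2 and 3, and report the multiplier at which the 15% conclusion changes.
- **Second estimate.** Pre-specify a 12-month cumulative FP estimate from time to first FP, with leavers censored, death as a competing event, and a log-log 97.5% upper limit compared with 15%. State the independent-censoring assumption and report it beside the complete-case Wilson result. Making it primary is optional. Death matters modestly: if 5–10% die within 12 months (assumed), an estimate that censors deaths and reads 13% corresponds to 12.7–12.4% actually having an FP.
- **Who counts.** State whether FP-free deaths and withdrawals are evaluable, and whether the target is the feature as used or the feature left ON. Count feature-OFF patients as FP-free only under the as-used target; otherwise censor at OFF. Against a left-ON target, counting them as FP-free repeats the downward error: with no loss, true 15% reads 14.6/14.3/13.9/13.5% at 5/10/15/20% OFF.

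In 4.3.1, reconcile the completers-only set with the censoring of withdrawals, for example by defining the 500 as patients whose Baseline or Baseline Upgrade visit was at least 6 months before the data cut.

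The cost is SAP wording and some extra analysis. Feature-OFF status by visit and deaths are already collected, and Kaplan-Meier with Greenwood variance is already planned in 4.3.1. The redacted sample-size text must be checked against the changes, above all if the new estimate becomes primary.

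### Primary safety endpoint, supportive imputation: a baseline comparison cannot show that data are not missing at random, yet it can trigger special imputation of a post hoc subgroup, and no MNAR sensitivity analysis is prespecified

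*Protocol*

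**What the plan says.** Section 4.3.2 sets the decision rule for the primary safety endpoint. "The primary analysis will be a complete case analysis": patients lost before the 12-month visit without an FP are dropped as non-evaluable, and the Wilson 95% upper bound must lie below 15%.

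The Imputation Analysis in the same section is supportive. It starts with a check: "A comparison of baseline characteristics of the subjects with missing data and those without missing data will be done", and its purpose is "to determine if there is evidence that the data are not missing at random". The plan adds the caveat that "it is not possible to determine that data are missing at random". It then states a consequence. "If the missing at random assumption is clearly violated by these comparisons", a subgroup may be found "who have to be imputed differently, such as assigning the worst score to patients in the sub-group". The remaining non-evaluable patients are imputed from a logistic model fitted to the complete cases. Its covariates are ischemic cardiomyopathy, four non-ischemic cardiomyopathy categories, "age, gender, QRS duration > 120ms and EF% at the time of enrollment". An FP is imputed only if the predicted probability exceeds 0.5.

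The legible text names no variables to compare, no test, no threshold for a clear violation, no rule for choosing the subgroup and no criterion for having resolved the difficulty. The SAP repeats the Protocol text.

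**The concern.** MAR allows missingness to depend on observed variables. If patients with a wide QRS drop out more often, MCAR is false, but MAR can still hold, and a model that conditions on QRS handles it. MAR fails when, given the observed data, missingness still depends on the unseen FP status. Baseline data cannot show this. The plan's caveat covers one direction only: it concedes that MAR cannot be confirmed, but treats baseline differences as able to refute it.

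If the authors meant MCAR, the trigger is still wrong, because the imputation model needs only MAR.

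The rule can therefore err in two ways. It may assign special scores, to a subgroup chosen after seeing the data, when covariate-based imputation would have been sound. It may also find no baseline difference while dropout depends on FP status, and then nothing further is done. The second error is the more serious, because it can leave an FP percentage that is too low. The bootstrap analysis in section 4.3.2 does not help, since it resamples evaluable patients with the same estimator.

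**Working it through.** The documents attach no figure to this rule, and the safety sample-size inputs are redacted, so there is no stated result to reproduce. Two checks follow, both on assumed inputs.

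**1. Does the comparison separate MAR from MNAR?** This was simulated with five baseline covariates and 150 runs per setting. The assumptions were N from 500 to 4,000, nominally 10% or 20% missing, full-data FP rates of about 8.5% to 12.5% and moderate covariate effects. A flag means that at least one covariate differs at the given level.

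| True mechanism | Flagged, any p<0.05 | Flagged, any p<0.001 |
|---|---|---|
| MCAR | 17–25% | 0–1% |
| MAR, N = 2,000–4,000 | 100% | 85–100% |
| MAR, N = 500 | 75–90% | 12–45% |
| MNAR (depends on FP status) | 21–33% | 0–2% |

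The flag responds to MAR and hardly separates MNAR from MCAR. At N = 4,000 with about 20% missing under MNAR, the complete-case rate averaged 8.8% against 11.5% in the full data. Under MAR in the same setting, imputing with the model probabilities gave 11.45% against 11.44%, so no special score was needed.

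**2. What can a worst-score trigger do to the imputed result?** N = 5,228 is total enrolment (Protocol section 4.5), used here as an upper limit. The 15% goal and the Wilson method are from section 4.3.2. The assumptions are 10% missing (523 missing, 4,705 evaluable), 30% of the missing given the worst score, and the other 70% imputed FP-free. The last follows the 0.5 cut-off: at such rates predicted probabilities rarely approach 0.5, and the largest seen in the simulated data sets was 0.36.

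Imputed rate = 0.90 × p + 0.10 × 0.30 × 1 + 0.10 × 0.70 × 0 = 0.90p + 0.03.

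Wilson upper bound = [p + z²/(2n) + z√(p(1−p)/n + z²/(4n²))] / (1 + z²/n), with z = 1.96.

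- p = 12%: 0.108 + 0.03 = 13.8%. Bound = (0.1380 + 0.0004 + 1.96 × 0.00477)/1.0007 = 14.8%.
- p = 13%: 0.117 + 0.03 = 14.7%. Bound = (0.1470 + 0.0004 + 1.96 × 0.00490)/1.0007 = 15.7%.

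| Complete-case rate | Complete-case bound (n = 4,705) | Imputed, no trigger (0.90p): rate, bound | Imputed, trigger (0.90p + 0.03): rate, bound |
|---|---|---|---|
| 12% | 13.0% | 10.8%, 11.7% | 13.8%, 14.8% (passes) |
| 13% | 14.0% | 11.7%, 12.6% | 14.7%, 15.7% (fails) |

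Under these inputs the trigger adds 3 percentage points to the imputed rate. Whether the bound crosses 15% depends on the starting rate, the missing fraction and the size of the subgroup.

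**The case against.** The strongest reply has five parts.

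- **The primary decision is elsewhere.** This stands. A reader might infer that the endpoint could be won or lost on this rule. It could not: the 15% goal is judged on the complete-case bound.
- **Worst score is only an example.** This stands. The plan says "such as assigning the worst score to patients in the sub-group" and applies special scores only if they resolve the difficulty. A reader might also infer that the imputed result could move in either direction. The only score the plan names can only raise the FP percentage, which works against the sponsor.
- **How often the rule would fire is unknown.** This stands. Nine independent covariates tested at 5% would give 1 − 0.95⁹ = 37% false alarms, but at p<0.001 the figure is 0.9%. Likewise, a 0.15 SD imbalance (523 against 4,705 patients) is detected with 90% power at 5% and 49% at p<0.001. The plan gives no threshold, the covariates are unlikely to be independent, and the safety population is smaller than total enrolment. None of these figures should be quoted as the plan's error rate.
- **A larger shift is not what the plan's rule produces.** If the other 70% of missing patients had FPs at the observed rate, 12% would become 0.97 × 0.12 + 0.03 = 14.6% (bound 15.6%, fails). The 0.5 cut-off would impute few or none of them as FP, so 13.8% is closer to the stated procedure.
- **The comparison has a use.** This stands. Arrhythmia history and primary ICD indication are collected (section 4.7) but are not in the imputation model. A difference there is a reason to add the variable, not to declare MNAR.

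What remains is the inference itself and the lack of any stated analysis that addresses MNAR.

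**Conclusion.** The point holds for the supportive imputation analysis. The trigger rests on evidence that cannot distinguish MAR from MNAR, the subgroup and its score are left to be chosen after the data are seen, and no prespecified MNAR sensitivity analysis appears in the legible text for this endpoint.

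The practical size is moderate. On the stated assumptions, a needless worst-score trigger leaves a 12% rate passing and turns a 13% rate into a fail in the supportive analysis only. That error is conservative. Missed outcome-dependent dropout is not, and the rule offers no safeguard against it. The missing fraction, subgroup share, FP rates and simulation settings are all assumed, because the documents do not give them. The 0.5 cut-off enters here only as the rule in force; its merits are a separate matter.

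**What to change.** In section 4.3.2, Imputation Analysis:

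1. Keep the baseline comparison as a description of who is missing and as a way to choose covariates for the imputation model.
2. Delete the statement that the comparison can show MAR to be violated, together with the data-driven subgroup and its special scores.
3. Prespecify a delta-adjusted tipping-point analysis for all non-evaluable patients, up to the bound where every one is counted as FP. Report the FP rate among missing patients at which the Wilson upper bound reaches 15%.

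With the illustrative inputs above, the Wilson bound at n = 5,228 reaches 15% when the overall rate is about 14.03%. The tipping rate in the missing is then (0.1403 − 0.108)/0.10 = 32% for a 12% complete-case rate, and (0.1403 − 0.117)/0.10 = 23% for 13%. Readers can judge whether such rates are plausible.

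The cost is SAP rewording and one short extra analysis, with no change to data collection or the primary test. The sponsor accepts that the sensitivity result may look less favourable.
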